4 STUDY DESIGN

4.1 General Description

This study is a multi-center, randomized, open-label clinical trial evaluating the efficacy and safety of ESG as an adjunct to life-style intervention for weight loss and improvement in obesity-related co-morbidities compared to lifestyle intervention alone in participants with a BMI ≥ 30 and ≤ 40 kg/m² who have failed to achieve and maintain weight loss with a non-surgical program.

Participants will be recruited from outpatient clinical weight loss clinics and from study-related institutional review board (IRB) approved advertisements. The cohort will include nor more than 50 patients without at least one of a) hypertension (HTN) on one or more anti-hypertensive medications or b) type II diabetes mellitus (DM) on oral agents only with HbA1c ≤ 9 . Enrollment will be tracked continuously and enrollment closed to non-DM, non-HTN patients after meeting the target for that group.

Two hundred eligible participants will be stratified into three groups (obesity, obesity-hypertension, and obesity-diabetes) and then block-randomized 1 to 1.5 to treatment (80 participants) and control (120 participants) groups alone as depicted in the diagram on page 16. All treatment group participants will undergo endoscopy and those without endoscopic contraindications will undergo the ESG. All control subjects will follow a low-calorie, healthy lifestyle intervention only for 12 months. After 12 months of lifestyle intervention, eligible control participants will crossover to receive the ESG. Those who had the ESG will undergo a repeat upper endoscopy at 52 weeks +- 4 weeks to evaluate the durability of the plications and re-tighten the ESG if needed with continued follow-up for 12 additional months.

The study will have two levels:

1. Level 1: the randomized study phase with primary outcomes for both groups evaluated at 12 months
2. Level 2: the crossover, non-randomized study phase with outcomes for a) the initial treatment group at 24 months post ESG (12 months after the re-tightening procedure) b) for the controlled cross-over group evaluated at 12 months after ESG

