7 STATISTICAL ANALYSIS

7.1 Power and Sample Size

The primary endpoint for power and sample size is %EWL at 12 months. The null hypothesis is no difference in mean %EWL between ESG and LS randomized arms ($H_0: \mu_t = \mu_c$ where μ_t is the average %EWL in the ESG group and μ_c is average %EWL in the LS group). We will perform a two-sided hypothesis test at alpha level 0.05 (alternative hypothesis $H_a: \mu_t \neq \mu_c$) Based on the published literature with the ESG technique a conservative presumption is 25% EWL in the ESG arm with a standard deviation (SD) of 30% at 12 months compared to 10% EWL on LS alone with SD of 5%. We plan a 1:1.5 randomization scheme that allocates 3 patients to LS for every 2 to ESG at the time of randomization. Based on a two-sample t-test with unequal variances and two-sided alpha=0.05, we would have 80% power to detect a difference of 15% in average %EWL between groups with 34 patients allocated to ESG and 51 randomized to LS. 90% power would require group sizes of 45 and 68, respectively. To allow for dropout, and more importantly, to power exploratory aims for obesity comorbidity subgroups, we propose the initial randomization of 200 patients – 80 to ESG and 120 to LS.

120 subjects are initially randomized to LS in level 1. Of these, we anticipate up to 20% will achieve a successful decrease of $\geq 25\%$ in %EWL through LS alone at 12 months. Further, we anticipate up to 20% may be lost to follow up or drop out prior to 12 month follow up. Thus, we anticipate at least 77 ($120 * 0.8 * 0.8$) subjects to continue to level 2 and be offered ESG. We will test the one-sample hypothesis (non-randomized) that of those offered ESG at 12 months, average change in %EWL will be at least 10%. Based on a one-sample t-test with two-sided alpha=0.05 and standard deviation at 24 months of 30%, 70 subjects completing ESG would have 98% power to detect an effect of 25% reduction in %EWL.

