7.2.2 Secondary Aims

Continuous secondary outcomes, including change in systolic and diastolic blood pressure and change in HbA1c, QOL questionnaires such as the SF-36, PHQ-9, and eating behavior scores will be compared between treatment arms using ANCOVA with adjustment for the same variables specified in the primary analysis.

Binary outcomes, including proportion with $\geq 25\%$ reduction in %EWL and incidence of esophagitis will be compared between treatment arms by Pearson Chi-square test.

Among patients randomized to the treatment ESG group, the association between the durability of plication at repeat endoscopy (score ≥ 1 on EGD grading system) and number of sutures required for re-tightening with change in EWL from 12 months to 24 months will be assessed using linear regression with adjustment for BMI, %EWL between randomization and 12 month follow up, HTN status, and DM status. This is an observational comparison.

Among patients randomized to the control LS arm, the percent EWL from the 12 month assessment to the 24 month assessment will be measured. This percentage will be compared to percent EWL in the same group with lifestyle intervention only in the first 12 months using a one sample t-test.

Among all subjects, %EWL will be compared at 24 months between initial and delayed ESG. However, this is not considered a comparison of randomized arms as follow up is not continued for patients with $\geq 25\%$ EWL from LS at 12 months.

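### The month-24 initial-versus-delayed ESG comparison mixes unequal time since ESG, one-sided re-tightening and an attendance filter that its caveat omits; a comparison at 12 months after ESG should be added

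*Combined protocol and SAP*

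**What the plan says.** Section 7.2.2 (Secondary Aims) states: "Among all subjects, %EWL will be compared at 24 months between initial and delayed ESG". It qualifies this at once: "However, this is not considered a comparison of randomized arms". The reason given is that "follow up is not continued for patients with" at least 25% EWL from lifestyle at 12 months.

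Section 4.1 describes Level 2 as "the crossover, non-randomized study phase" and sets its assessment times. One group is "the initial treatment group at 24 months post ESG (12 months after the re-tightening procedure"); the other is "for the controlled cross-over group evaluated at 12 months after ESG".

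Three other places bear on who is compared and what they received:

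- Section 5.5.1.1.1 makes crossover conditional on attending at least 75% of Level 1 visits, among other criteria.
- Section 5.5.1.1.2 gives initial-arm patients not above 25% EWL a repeat endoscopy, with re-tightening according to the sleeve grade. The crossover schedule in Section 5.6 has no such step.
- Section 5.6 has a year-2 schedule for LS-randomized patients only if they cross over.

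For this comparison Section 7.2.2 names no test, no adjustment set, no baseline weight for %EWL and no alignment on time since ESG.

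**The concern.** This is the only between-arm comparison planned after month 12, in a trial whose rationale (Section 2.3) is long-term efficacy. Two questions could sensibly be asked of these data:

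1. Does ESG work as well after a year of lifestyle treatment as it does when given first? This needs both groups at the same time since ESG, before any second procedure.
2. How do the two randomized strategies compare at month 24? This needs every LS-randomized patient to be weighed at month 24.

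The planned contrast meets neither requirement. Its caveat names only the loss of LS successes, so a reader of the results would not learn that the groups also differ in time since ESG, access to re-tightening and attendance. A month-24 weight that was never taken cannot be recovered later by analysis.

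**Working it through.** **Plan's own count.** Section 7.1 takes 120 controls, up to 20% lost and up to 20% succeeding on lifestyle: 120 × 0.8 × 0.8 = 76.8, which matches "we anticipate at least 77". With dropout taken first, 120 × 0.8 = 96 are retained, 96 × 0.2 ≈ 19 are LS successes, and 77 remain (64% of 120). The attendance requirement is not in this count.

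**The groups at month 24**

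| | Initial ESG | Delayed ESG |
|---|---|---|
| Time since ESG | 24 months | 12 months |
| Re-tightening | possible from about month 12 | not scheduled |
| Selected on LS response | no | yes |
| Selected on 75% attendance | no | yes |
| Prior lifestyle-only year | no | yes |

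If ESG %EWL is normal with the Section 7.1 mean of 25 and SD of 30, half of the initial arm (80 × 0.5 = 40) is not above 25% and qualifies for repeat endoscopy. How many are then re-tightened depends on the sleeve grade.

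**Size of the selection on LS response.** Assume LS %EWL at month 12 is normal with mean 10 (Section 7.1). With k = 15/SD, the mean of those below 25% is 10 − SD × φ(k)/Φ(k).

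- Stated SD of 5: k = 3 and P(≥25%) = 0.00135, or 120 × 0.00135 ≈ 0.2 patients. The mean of those kept is 9.98, so there is almost no selection.
- Success rate of 20%: SD = 15/0.8416 = 17.8. Mean of those kept = 10 − 17.82 × 0.280/0.8 = 3.8; mean of those dropped = 10 + 17.82 × 0.280/0.2 = 34.9. The kept group is about 6 points below the full arm at month 12.
- In between: SD 10 gives 6.7% successes and a kept mean of 8.6; SD 15 gives 15.9% and 5.7.

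These are month-12 lifestyle differences. Their effect on later ESG response depends on the correlation ρ between the two responses, which the documents do not give. With ESG SD 30 and 20% successes, the shift is 30 × ρ × 0.280/0.8 = 10.5ρ: zero at ρ = 0, about 3 points at 0.3 and about 5 at 0.5.

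**Size of the time difference.** Section 2.2 reports 18% TBWL at 12 months and 20% at 18 months; the documents give no 24-month figure. Relative to an ideal BMI of 25, 2 points of TBWL equal 2 ÷ ((BMI − 25)/BMI) points of EWL: 12 at BMI 30, 7 at BMI 35 and 5.3 at BMI 40.

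Suppose ESG works equally well in both groups and only time since ESG differs. With 80 versus 77 patients and an assumed SD of 30 in each, SE = √(900/80 + 900/77) = 4.79. Shifts of 5, 7 and 12 points then give p < 0.05 in about 18%, 31% and 70% of trials. With 80 × 0.8 = 64 initial patients the figures are about 16%, 28% and 65%.

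**Direction.** Losing LS successes tends to lower the delayed group if LS and ESG responses are positively correlated. Further loss between months 12 and 24 would favour the initial group, and regain would favour the delayed group. If %EWL is counted from randomization, the delayed group also carries its lifestyle-year loss. The net sign is not determined.

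**Who is lost.** Section 5.5.1.1.1 admits controls who have not reached 25% EWL, or whose BMI is still 30 to 40. After 25% EWL, BMI is 0.75 × baseline + 6.25, which is at least 30 when baseline BMI is at least (30 − 6.25)/0.75 = 31.7. Read literally, many LS successes could cross over, contrary to Section 7.2.2.

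**The case against.** The plan is candid about the main limitation. It calls the comparison non-randomized in the sentence after it is introduced, labels Level 2 the same way, and states both times since ESG. The contrast is not an endpoint in Section 4.2.1 and has no hypothesis or power calculation. A reader might infer that the plan intends to credit the difference to the timing of ESG; no passage says so. All of this stands, and it makes this a secondary-analysis point.

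A reader might also call the 24-against-12-month gap a bias in itself. That goes too far. At a common time from randomization, the gap and the re-tightening belong to the strategy of having ESG first. They confound only the question of whether later ESG works as well. But the strategy comparison needs all LS-randomized patients, and the plan does not follow them all.

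Nor is the 6-point selection figure a bias at month 24. It is a month-12 lifestyle difference, it treats an upper bound of 20% as the actual rate, and its SD is more than three times the stated one. The stated SD of 5 and a 20% success rate cannot both hold under a normal distribution with mean 10, so only a range can be given.

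Finally, comparing at 12 months after ESG does not remove selection on LS response and attendance. That is correct, and the result must be labelled accordingly.

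**Conclusion.** The point holds as a secondary-analysis improvement. The caveat covers one source of non-comparability and leaves out unequal time since ESG, one-sided re-tightening and the attendance filter. As planned, the contrast answers neither of the two useful questions.

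The selection shift at month 12 runs from near zero (SD 5) to about 6 %EWL points (20% successes, normal distribution). The time-since-ESG shift could be about 5 to 12 points if the reported change from 12 to 18 months is a guide; that is an assumption, since the documents give nothing at 24 months. The time and re-tightening mismatch remains whichever LS SD is right. The direction of the net effect is unknown.

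**What to change.** **1. Comparison at equal time since ESG.** Make the main initial-versus-delayed contrast %EWL at 12 months after ESG in both groups, each measured from its own procedure-day weight and before any re-tightening.

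- Count time from the ESG date and state a window. Section 4.2.1 ties the week-52 visit to 12 months from randomization, and ESG may follow randomization by up to 30 days (Section 5.4). That weight may therefore be taken only 364 − 30 = 334 days (about 48 weeks) after ESG.
- Adjust for the covariates of Section 7.2.1 and label the result observational, because the delayed group remains selected on LS response and attendance.
- If the month-24 contrast is kept, extend its caveat to time since ESG, re-tightening and attendance, and state the baseline weight.

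Cost: mainly SAP wording. Procedure-day and week-52 weights are scheduled in both groups, and Table 2 adds a weight at re-tightening or at week 60.

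**2. Comparison of randomized strategies, where feasible.** Record one weight at 24 months from randomization for every LS-randomized patient, including LS successes and those who do not cross over. Compare the arms as randomized: ESG first, against lifestyle first with ESG later if eligible. Handle dropout with the missing-at-random and multiple-imputation approach of Section 7.3. State that this compares strategies and is not ESG against lifestyle at 24 months, since most retained controls would have been offered ESG by then.

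Cost: one weight visit for about 19 LS successes (on the plan's rates) plus the non-crossovers, and a consent and schedule amendment.

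**3. Reconcile** Sections 5.5.1.1.1 and 7.2.2 on whether LS successes may cross over, so that the delayed group is defined.

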7.2.3 Secondary Analyses

A per-protocol analysis will compare ESG to LS randomized groups among protocol adherent patients – here, defined among ESG randomized patients as those actually receiving the procedure and making $\geq 80\%$ follow-up visit in both treatment and control groups. Modified ITT will be considered the primary approach for all efficacy analyses, and will include patients who actually receive the ESG or started the life-style program regardless of adherence to follow-up visits. Safety endpoints and adverse events may be evaluated based on treated group (per-protocol).

Additional analyses may assess the moderating effect of HTN and DM on the effect of ESG vs LS at 12 months. Linear regression will include an interaction between HTN (or DM) and randomized group to determine the effect of ESG in subgroups and whether the effect is different between HTN and non-HTN (also, separately, DM and non-DM) patients.

Additional outcomes and analyses not specified here are considered exploratory and post-hoc and will be clearly identified as such in any publications.

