2.2 Clinical Data to Date

The feasibility of ESG was first demonstrated in humans in the US in 2013.²⁰ Since then, the technique has gained wide clinical adoption in the US and world-wide with more than 2000 cases performed. Multiple single-arm prospective and retrospective studies have demonstrated the safety and minimally invasive nature of the technique and reported %TBWL of about 18% at 12 months.^{21, 22} Furthermore, studies have demonstrated physiologic perturbations resulting from creation of the ESG and its association with increased satiation and metabolic effects that are potentially important to control the metabolic dysregulation associated with obesity.²³ In a recent multicenter study of 248 patients enrolled at Mayo Clinic, Cornell Medical Center, and Madrid Hospital, ESG was associated with 18% and 20% TBWL at 12 and 18 months, respectively²³. More importantly, in this large series, incidence of serious adverse events (SAE) was only 2% and none of these SAEs required any surgical intervention. No mortality was reported.

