2.3 Rationale

A joint task force convened by the ASGE and the ASMBs defined safety of efficacy threshold that endoscopic bariatric therapies, such as ESG, need to meet before societies recommend their wide-spread adoption. These thresholds are as follows: EBTs intended as a primary obesity intervention in patients with mild to moderate obesity should achieve a mean minimum threshold of 25% excess weight loss (%EWL) measured at 12 months (calculated based on an ideal BMI of 25mg/kg²). In addition to the absolute threshold of weight loss, the mean %EWL difference between the procedure and control should be a minimum of 15% EWL and be statistically significant. Finally, the risk associated with EBT should equate to a 5%

incidence of serious adverse events or less. Based on this consensus statement, an endoscopic intervention that meets these established thresholds should be considered appropriate to incorporate into wide-spread clinical practice presuming that the appropriate training and credentialing in that EBT has been achieved^{24, 25}.

Despite the excellent clinical experience with ESG, no randomized clinical trials have been performed to evaluate the long-term efficacy of the technique over life-style intervention in producing significant long-term weight loss, improving obesity associated co-morbidities, and meeting the societal thresholds. Furthermore, Level 1 evidence is needed to further advance this promising technique and achieve wide-spread adoption. Therefore, we are proposing a randomized controlled trial to evaluate the long-term safety and efficacy of ESG in meeting efficacy endpoints set forth in a consensus statement by relevant societies (American Society of Gastrointestinal Endoscopy [ASGE] and American Society of Metabolic and Bariatric Surgery [ASMBS]) and its impact on obesity related co-morbidities in patients with obesity and body mass index (BMI) between 30-40 kg/m².

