3 STUDY OBJECTIVES

1. Assess if ESG achieves safety and efficacy threshold as defined by joint societal consensus statement by ASGE and ASMBS
2. Assess the impact of ESG on obesity related co-morbidities (Hypertension and Diabetes)
3. Assess the mid-term durability of weight loss achieved by ESG at 24 months.
4. Assess the impact of re-tightening the ESG on weight loss trajectory.

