4.2.2 Safety

- The incidence, frequency, and severity of adverse events related to treatment with the device will be reported.
- <5% rate of serious adverse events related to the device or procedure (as determined by the site PI). Serious adverse events are classified in the Adverse Events table (page 25)

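### The denominator for the 5% serious-adverse-event criterion is loosely defined: the safety sentence labels the treated group per-protocol, a set that carries an 80% visit rule and gives crossover recipients no stated place

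*Combined protocol and SAP*

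**What the plan says.** Section 3 makes the societal thresholds the first objective: "Assess if ESG achieves safety and efficacy threshold as defined by joint societal consensus statement by ASGE and ASMBS". Section 2.3 gives the safety threshold as a 5% "incidence of serious adverse events or less". Section 4.2.2 restates it as an endpoint, "<5% rate of serious adverse events related to the device or procedure (as determined by the site PI"), and names no denominator.

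The population for safety appears once, in Section 7.2.3: "Safety endpoints and adverse events may be evaluated based on treated group (per-protocol"). The same paragraph holds the only per-protocol definition. It opens "A per-protocol analysis will compare ESG to LS randomized groups among protocol adherent patients" and continues "here, defined among ESG randomized patients as those actually receiving the procedure and making" at least 80% of follow-up visits, with the visit part applied to both arms. The modified intent-to-treat set, which ignores attendance, is specified for efficacy. No separate safety or as-treated set is defined.

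Section 4.1 lets eligible controls receive ESG after 12 months, and Section 7.1 expects at least 77 of them to be offered it. Section 5.7 allows investigators to withdraw participants for safety or because of adverse device effects.

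**The concern.** The words for the treated group point to everyone who received ESG. The parenthesis points to a set restricted by attendance. The verb is permissive, so neither is binding.

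An attendance condition suits a supportive efficacy analysis. It suits a safety rate poorly, because a patient harmed early may stop attending for that reason. If the parenthesis is followed literally, such a patient could drop out of both numerator and denominator. The rate is then biased downward only if patients with SAEs miss the visit rule more often than other ESG recipients; otherwise it is merely less precise.

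The second gap is the crossover group. The per-protocol set serves the randomized comparison of ESG with lifestyle intervention, so it does not say whether a control who later receives ESG counts. Including these patients could nearly double the denominator.

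At stake is a pass/fail statement on a threshold that the first objective tests. With the wording left open, the denominator could be settled after the events are known.

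**Working it through.** **Inputs.** ESG arm 80 and control arm 120 (7.1). Criterion below 5% (4.2.2) or 5% or less (2.3). Prior SAE rate: "incidence of serious adverse events (SAE) was only 2" per cent (2.2). Up to 20% loss by 12 months, stated for the lifestyle arm only (7.1). The plan gives no expected share of ESG patients missing the visit rule, so 20% (16 of 80) is an assumption, with 10% and 30% as a range. I count patients with at least one related SAE.

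**The plan's own figure.** Crossovers offered ESG: 120 × 0.8 × 0.8 = 76.8, or 77, as stated. The plan gives no calculation for the SAE criterion.

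**What the visit rule could require.** The plan does not say which visits form the base of the 80%. Section 5.5 gives 12 visits in year 1: 0.8 × 12 = 9.6, so 10 visits, and visit 10 is Week 42. Sections 7.2.1 and 7.3 count 11: 0.8 × 11 = 8.8, so 9 visits, and visit 9 is Week 36. If only visits due while the patient is in the study are counted, early withdrawals are not removed as such and the rule affects poor attenders only.

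**Largest passing count.** Below 5%: 3 of 80 (3.75%), 3 of 64 (4.69%), 2 of 56 (3.57%), 7 of 157 (4.46%). With 5% or less, the limit for 80 becomes 4; the others are unchanged.

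**Boundary case, 16 of 80 removed at random.** With 4 patients with SAEs, 4/80 = 5.0% fails the strict limit. All four stay among the 64 with probability C(64,4)/C(80,4) = 0.402, giving 4/64 = 6.25%. Otherwise, with probability 0.598, at most three stay and the rate is at most 3/64 = 4.69%, a pass. With 5 patients with SAEs, the chance that at most three stay is 0.260.

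**Overall chance of a changed verdict.** Sum over k of Binomial(80, p) × hypergeometric. At p = 2%: 0.0545 × 0.598 + 0.0169 × 0.260 + 0.0043 × 0.091 + smaller terms = 0.037.

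| Criterion, number missing | 2% rate: fail→pass / pass→fail | 5% rate: fail→pass / pass→fail |
|---|---|---|
| below 5%, 8 | 0.020 / 0 | 0.084 / 0 |
| below 5%, 16 | 0.037 / 0 | 0.173 / 0 |
| below 5%, 24 | 0.022 / 0.047 | 0.103 / 0.067 |
| 5% or less, 16 | 0.005 / 0.022 | 0.053 / 0.081 |

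With 8 or 16 missing, the strict limit stays at 3, so changes run only from fail to pass. With 24 missing it falls to 2 and changes run both ways.

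**Informative loss (pure assumption).** If patients with SAEs miss the rule 40% of the time and the limit stays at 3, the fail-to-pass chance is 0.061 at 2% and 0.352 at 5%.

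**Crossovers.** Assume that all 77 offered ESG receive it, with the same SAE rate. Four SAEs among the 80 and three among the 77 fail on 80 (5.0%) but pass pooled (7/157 = 4.46%). Three and five pass on 80 (3.75%) but fail pooled (8/157 = 5.10%). Under the strict limit, the verdicts on 80 and on 157 differ with probability 0.071 at 2% and 0.246 at 5%; under 5% or less, 0.024 and 0.262. Fewer than 77 may actually receive ESG: Section 7.1 uses 70 completers for power.

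**The case against.** The as-treated reading is the natural one. The noun in the safety sentence is the treated group, and the visit rule is introduced as a definition for the randomized efficacy comparison. Section 4.2.2 makes reporting compulsory with no attendance filter: "The incidence, frequency, and severity of adverse events related to treatment with the device will be reported". The adverse-event form is scheduled throughout crossover follow-up, and the monitoring committee reviews events. This stands. A reader might infer that SAEs would go unseen, or that the plan requires an attendance filter on all safety data; the documents support neither. The question concerns one denominator.

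A reader might also infer that the per-protocol definition names only ESG-randomized patients and so expressly excludes crossovers. It does not. Only the receipt-of-procedure condition is tied to that arm, and the visit condition covers both arms. Crossover recipients are simply not assigned to the denominator or excluded from it.

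The attendance loss is assumed, and random loss produces no expected bias. The plan also attaches no test or confidence bound to the 5% figure, and 3/80 has a 95% interval of 0.8% to 10.6%, so one event more or less is within noise. These points limit the weight of the concern. They do not supply a denominator, and as written the criterion is a point threshold that one event can decide.

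**Conclusion.** The wording needs correction, but the severity is minor. The safety sentence carries a label whose only definition includes an 80% visit rule, no other section defines a safety set, and the place of crossover recipients is unstated.

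At the plan's own 2% SAE rate the risk is small: about a 4% chance of a changed verdict if 16 of 80 miss the rule at random, and about 7% between 80 and 157 patients under the strict limit. At a true rate of 5% these become about 17% and 25%. All of these rest on assumed attendance, or on full crossover uptake with an equal SAE rate.

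It is tempting to conclude that the wording favours the device. That is not established: the direction depends on the attendance loss, on which form of the limit applies, and on whether patients with SAEs attend less.

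**What to change.** In Section 7.2.3, delete the per-protocol parenthesis and change the permissive verb to a commitment. Define the safety set as every participant in whom ESG was attempted, by treatment received and regardless of visit attendance or withdrawal, and name it in Section 4.2.2 as the denominator for the SAE criterion. Show randomized and crossover recipients separately and pooled, and state in advance which of these decides the criterion.

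Reconcile the strict limit in Section 4.2.2 with the inclusive one in Section 2.3, since 4/80 falls exactly on that boundary.

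The cost is a few lines of text and no new data. The downside is that the SAE rate may be slightly less favourable than in a visit-adherent set. If as-treated was always intended, the edit only confirms it.
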